Adverse Event	AE	Any untoward medical occurrence in a participant or clinical trial subject participating in the trial which does not necessarily have a causal relationship with the intervention received
Related Event		An event which resulted from the administration of any of the research procedures
Serious Adverse Event	SAE	An untoward occurrence that: 
 • Results in death • Is life-threatening • Requires hospitalisation or prolongation of existing hospitalisation (with exceptions – see section 9.2) • Results in persistent or significant disability or incapacity • Or is otherwise considered medically significant by the Investigator
Unexpected and Related Event		An event which meets the definition of both an Unexpected Event and a Related Event

Unexpected Event		The type of event that is not listed in the protocol as an expected occurrence
Source data		All information in original records and certified copies of original records of clinical findings, observations, or other activities in a clinical trial necessary for the reconstruction and evaluation of the trial
Birmingham Clinical Trials Unit	BCTU	The co-ordinating centre for the trial

TRIAL SUMMARY

Title Laparoscopic Versus Abdominal hysterectomy (LAVA) trial

Objectives To determine the clinical and cost-effectiveness of laparoscopic hysterectomy compared to open abdominal hysterectomy for women with a benign gynaecological condition

Trial Design A parallel, open, non-inferiority, multicentre, randomised controlled, expertise-based surgery trial with integrated health economic evaluation and an internal pilot with an embedded qualitative process evaluation.

Participant Population and Sample Size 3250 women who require a hysterectomy for a benign gynaecological condition

Eligibility Criteria Women with benign gynaecological conditions requiring a hysterectomy and who are suitable for either surgical technique are eligible for inclusion. The intervention is laparoscopic hysterectomy and the comparator is open, abdominal hysterectomy.

Interventions Laparoscopic hysterectomy compared to open abdominal hysterectomy

Outcome Measures Summary (full details given in section 8.1)

- **Primary** – Major surgical complications up to six completed weeks post-surgery
- **Key secondary** - Time from surgery to resumption of usual activities using the personalised PROMIS-SF (Patient-Reported Outcomes Measurement Information System Physical Function) questionnaire

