8.1.2. Primary Outcome

Major surgical complications. These will be objectively ascribed and largely in accordance with the validated and widely used Clavien-Dindo classification of surgical complications²⁴. They will be defined as any of the following up to and including six full weeks post-surgery: i) all Clavien-Dindo grade III-V complications ii) Clavien-Dindo grade II complications of pulmonary embolus or blood transfusion or; iii) haemorrhage \geq 1L or; iv) major adverse anaesthetic event (see table below).

The most commonly anticipated major surgical complications are:

- Haemorrhage \geq 1 L
- Blood transfusion
- Bladder injury
- Ureteric injury
- Bowel injury
- Vascular injury
- Unplanned removal of any other organ
- Any other complication not covered requiring surgical, endoscopic or radiological intervention
- Pelvic haematoma requiring radiological or surgical intervention
- Pelvic abscess requiring radiological or surgical intervention
- Life-threatening complication requiring admission to HDU/ITU

However, other less common major surgical or anaesthetic complications may arise and these will be ascribed in accordance with the appropriate Clavien-Dindo classification.

Definition of major surgical complications in the LAVA trial

Major haemorrhage	Haemorrhage \geq 1L
Clavien-Dindo grade II	Pulmonary embolus, blood transfusion
Clavien-Dindo grade III	Complication requiring surgical, endoscopic or radiological intervention
Clavien-Dindo grade IV	Life-threatening complication requiring management on a High Dependency Unit (HDU) / intensive therapy unit (ITU)*
Clavien-Dindo grade V	Death
Major anaesthetic event	Anaphylaxis, awareness, nerve injury (including epidural/spinal anaesthesia), hypoxic brain injury, malignant hyperthermia, iatrogenic complication (e.g. pneumothorax from central line, limb ischaemia from arterial line)

*Non-life threatening elective or precautionary admission to an HDU (e.g. because of medical co-morbidities) post-operatively will not be considered a grade IV complication.

Complication data occurring during and up to 6 weeks following hysterectomy will be collected from the relevant case report forms completed by the local research team:

- Day of Surgery CRF
 - Detailing the type of major peri-operative complications
- Post-operative inpatient CRF
 - Detailing the type and timing of major surgical complications occurring during inpatient stay up until hospital discharge)

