8.1.3.2 Other secondary outcomes

- Surgical outcomes:
 - Duration of operation, (minutes)
 - Estimated blood loss, (ml)
- In hospital stay:
 - In hospital post-operative pain using a Numerical rating scale (NRS) (with 0 indicating no pain to 10 indicating maximum pain)*, measured daily
 - Total analgesia use*
 - Overall quality of recovery score taken from the Quality of Recovery 15 (QoR-15) questionnaire²⁵ (with 0 indicating worst recovery and 10 indicating best recovery), measured at approximately 24 hours post-operation*
 - Time from operation to discharge in days (the day of operation will be assumed to be day 1. i.e. discharge on day 2 = 2 days). Each part of a day will count as a whole day, e.g. discharge after 2.5 days = 3 days)
- Up to 14 days after surgery:
 - post-operative pain using a Numerical rating scale (NRS) (with 0 indicating no pain to 10 indicating maximum pain), measured daily
 - Total analgesia use

- Up to 6 weeks post-surgery:
 - Minor complications (Haemorrhage 500mL to ≤ 1 L; pyrexia [presumed infection] requiring antibiotics; pain uncontrolled with usual analgesic management; urinary retention requiring re-catheterization; catheterisation for longer than 72 hrs; pelvic haematoma NOT requiring radiological or surgical intervention; pelvic abscess NOT requiring radiological or surgical intervention; wound infections/complications managed at the bedside or on the ward)
 - Representation to hospital
 - Readmission to hospital
 - Use of health services
 - Time away from normal activities

- 6 weeks post-surgery:
 - Quality of life score using EuroQol-5D-5L questionnaire²⁶ (with -0.285 indicating worst possible value and 1.0 as best possible value)
 - Quality of life score using EuroQol-5D-5L visual analogue scale (with 0 indicating worst possible score and 100 as best possible score)

- 12 weeks post-surgery:
 - Quality of life score using EuroQol-5D-5L questionnaire²⁶ (with -0.285 indicating worst possible value and 1.0 as best possible value)
 - Quality of life score using EuroQol-5D-5L visual analogue scale (with 0 indicating worst possible score and 100 as best possible score)
 - Time from surgery to work (if working) in days
 - Work productivity and activity impairment scores using WPAI-GH questionnaire²⁷ (absenteeism score; presenteeism score; work productivity loss score; activity impairment score – all scored 0 good to 100 bad) at 12 weeks only

- 12/24/36 months post-surgery:**

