9.2. Adverse Events (AE) non-CTIMPs

All medical occurrences which meet the definition of an AE should be reported. Please note this includes abnormal laboratory findings.

Peri-operative and post-operative complications experienced by the participants are the primary outcomes of the LAVA study. Complications arising from the interventions will be collected on the relevant CRFs.

As these events are well characterised, it is highly unlikely that this trial will reveal any new safety information relating to this intervention. The recording of selected AEs will therefore not affect the safety of participants or the aims of the trial. As such the following will not be classed as adverse events and so do not need to be reported as AEs:

- Haemorrhage \geq 1L
- Surgical Complications (any factor that comprises the Clavien-Dindo grade [II-IV] with or without hospitalisation or prolongation of existing hospitalisation)
- Anaesthetic complications
- Additional Medication required above that normally expected
- Emergency presentations / admissions
- Routine re-presentations / admissions for pre-planned events
- Prolonged hospitalisation without an associated adverse event
- Vaginal bleeding
- Pelvic organ prolapse
- Abdominal pain [cyclical / non-cyclical, and dyspareunia]
- Conditions / symptoms arising from altered bowel or bladder function

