9.3. Serious Adverse Adverts (SAE) non-CTIMPs

All events which meet the definition of serious, and that are not excluded above, will be collected and recorded as SAEs. These will be reported to the trials office immediately and within 24 hours of being made aware of the event.

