13.2. Analysis of Outcome Measures

A separate Statistical Analysis Plan will be produced and will provide a more comprehensive description of the planned statistical analyses. A brief outline of these analyses is given below. The primary comparison groups will be composed of those treated with laparoscopic hysterectomy versus those treated with open, abdominal hysterectomy. For all outcomes, analyses will be based on the intention to treat principle, i.e. all participants will be analysed in the treatment group to which they were randomised irrespective of compliance or other protocol deviation. For the primary outcome, given the nature of the non-inferiority design, supportive per-protocol and CACE analyses³⁸ will be considered alongside the intention-to-treat population. All outcomes will be adjusted for the minimisation variables listed in Section 6.3 where possible.

For all major outcome measures, summary statistics and differences between groups, e.g. relative risks, will be presented with 95% confidence intervals. For the primary outcome, this is equivalent to a one-sided 97.5% confidence interval and hence

conservative in terms of the non-inferiority margin. For the trial to declare non-inferiority of the laparoscopic approach, the lower margin of the absolute risk difference (see 13.2.1 for calculation method) confidence interval must not exceed 3%.

For the key secondary outcome of time from surgery to resumption of usual activities, we will incorporate a conditional hierarchical approach to interpretation of the 95% confidence interval to ensure we appropriately control for the overall rate of type I error³⁹. If the primary outcome meets its non-inferiority objective we will then proceed to examine any differences between the two approaches for this outcome. For example, if the 95% confidence interval does not contain 1 (and favours laparoscopic) we will declare superiority of the laparoscopic approach.

Other secondary outcomes will be considered as exploratory; no adjustment for multiple comparisons will be made and hence significance should not be inferred from the confidence interval width. The exception is Serious Adverse Events may be subject to statistical testing without adjustment for multiple testing, as adjustment for multiplicity is counterproductive for considerations of safety.³⁹

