13.2.2. Secondary Outcome Measures

The key secondary outcome of time from surgery to resumption of normal activities will be analysed using a mixed effects ('frailty') Cox Proportional Hazard model⁴⁰, allowing the same minimisation variables and incorporating parameters for both centre and surgeon.

Linear regression models will be used to analyse response from continuous outcome measures such as, e.g. participant reported questionnaires, duration of surgery and pain via NRS; mean differences and 95% confidence intervals will be produced. Other binary and time-to-event analyses will be considered in the same fashion as the primary and key secondary outcomes. Satisfaction responses will be analysed using ordinal logistic regression. Serious adverse events will be summarised and analysed using a chi-squared test. Analgesia use will be summarised but not formally analysed. Appropriate summary statistics split by group will be presented for each outcome (e.g. proportions/percentages, mean/standard deviation or median/interquartile range).

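### The tested SAE outcome is a residual set: it omits most serious surgical complications yet can admit milder, stay-prolonging forms of some of them, so it cannot be read alone as a comparison of serious harm

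*Protocol*

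**What the plan says.** The definitions table at the front of the protocol makes an event serious if, among other criteria, it "Requires hospitalisation or prolongation of existing hospitalisation (with exceptions – see section 9.2").

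Section 9.2 states that "the following will not be classed as adverse events and so do not need to be reported as AEs". The list includes haemorrhage of at least 1 L, anaesthetic complications and "Surgical Complications (any factor that comprises the Clavien-Dindo grade [II-IV] with or without hospitalisation or prolongation of existing hospitalisation"). It also includes milder items: extra medication, emergency presentations or admissions, vaginal bleeding, abdominal pain, and bowel or bladder symptoms. Prolonged hospitalisation is listed only where no adverse event is associated with it.

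Section 9.3 then fixes the SAE set: "All events which meet the definition of serious, and that are not excluded above, will be collected and recorded as SAEs".

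Section 8.1.3.2 names serious adverse events as a secondary outcome throughout the trial. Section 13.2.2 says "Serious adverse events will be summarised and analysed using a chi-squared test". Section 13.2 treats the other secondary outcomes as exploratory, with no inference of significance, and adds: "The exception is Serious Adverse Events may be subject to statistical testing without adjustment for multiple testing".

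**The concern.** The reason given in section 9.2 is sensible for reporting: complications are well characterised, are the primary outcome and go on their own CRFs. The difficulty is that the same filter also defines a between-arm outcome that is tested. The list names grades II to IV and large bleeds but not grade I or smaller bleeds. For some complications the milder form can therefore be counted and the severe form cannot.

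The protocol expects the arms to differ in kind of complication (section 1.1: wound infection and pain after abdominal surgery, more urological complications after laparoscopic surgery) and in usual length of stay (section 1.2), which affects what counts as prolongation. A difference in this residual count could appear when total serious harm is equal, or fail to appear when it differs. The direction cannot be predicted. Because this outcome alone among the other secondary outcomes escapes the no-significance rule, a p-value from it is likely to be read as a statement about safety.

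**Working it through.** **1. Applying the rules to paired events.** Inputs: the seriousness definition, the section 9.2 list, the section 9.3 rule, and the minor and major complications in sections 8.1.3.2 and 8.1.2.

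| Complication | Milder form, prolonging the stay | Severe form |
|---|---|---|
| Bleeding | Below 1 L, no transfusion, grade I: not listed, so an SAE | At least 1 L: listed, so not an AE |
| Pelvic haematoma | "pelvic haematoma NOT requiring radiological or surgical intervention", if grade I: not listed, so an SAE | "Pelvic haematoma requiring radiological or surgical intervention" (grade III): listed, so not an AE |
| Wound problem | Managed at the bedside, if grade I: not listed, so an SAE | Needing surgery (grade III): listed, so not an AE |

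The stay-related item in section 9.2 does not rescue the left-hand column, because in each case there is an associated event.

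**2. How far this extends.** Not to all minor complications. Uncontrolled pain, urinary retention or long catheterisation, and pyrexia needing antibiotics plausibly fall under the listed pain, bladder, medication or grade II items. Listed emergency admissions close much of the readmission route. Death (grade V) is not listed and stays an SAE.

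**3. Time.** The primary outcome ends at six full weeks (section 8.1.2). The section 9.2 list has no time limit, and AE reporting runs until the woman exits the study (section 9.4). A grade III complication at week 8 is therefore neither a primary event nor an SAE. Later hospital contacts are collected for the economic evaluation and are not reported separately (section 8.1.3.2).

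**4. Scale of what is left out.** Section 13.1 assumes 6% major complications in the control group. With 1625 per arm, 0.06 × 1625 = 97.5 women, nearly all outside the SAE count. The section 13.1 figures reproduce: 1317 per arm, 2634 in total; × (1 + 8 × 0.02) = 3055; ÷ 0.94 = 3250. They are background only; the protocol gives no SAE rate.

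**5. Illustration of a false difference (all rates assumed, 3055/2 = 1527.5 per arm).** z = d / √[2p̄(1 − p̄)/n].
- Milder stay-prolonging events 2% abdominal v 1% laparoscopic; excluded serious complications 4% v 5%. Totals: 6% in each arm. The test sees 2% v 1%: z = 0.01/√(2 × 0.015 × 0.985/1527.5) = 0.01/0.00440 = 2.27, p = 0.023.
- 1.5% v 0.5%, with 3% v 4% excluded. Totals: 4.5% in each arm. z = 0.01/0.00360 = 2.78, p = 0.005.
- Half the first pair, 1% v 0.5%: z = 0.005/0.00312 = 1.60, p = 0.11.

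**6. Illustration of a hidden difference (assumed, 1625 per arm).** Major complications 6% v 9%, all taken as serious; other SAEs equal at 1% to 4% and in different women. Power = Φ[(d − 1.96·s₀)/s₁], where s₀ and s₁ are the pooled and unpooled standard errors.
- Complications counted, 7% v 10%: Φ[(0.03 − 1.96 × 0.00978)/0.00977] = 87%.
- Complications counted, 10% v 13%: Φ[(0.03 − 1.96 × 0.01119)/0.01118] = 76.5%, about 77%.
- Complications excluded: the arms are equal on what is counted, so the test rejects only at its 5% error rate.

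**The case against.** The strongest reply is that the carve-out is deliberate and the harm is visible elsewhere. Major complications to six weeks are the primary outcome, with a formal confidence-interval rule. Minor complications are a separate secondary outcome. The DMC is likely to see the primary outcome as well as SAEs (section 13.3). The test is worded as something that may be done, is outside the hierarchy, and decides no trial conclusion. In the illustrations, excluded events that meet the primary definition would show up in the primary analysis.

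Most of this stands, and it limits the point. It does not remove it: the protocol still fixes a tested outcome whose content does not match its name, and the primary outcome gives no cover after six weeks.

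A reader might infer more: that the list removes complications only at the severe end, that severity is reversed throughout, or that the SAE comparison contains no serious harm. The text does not support this. Several mild items are also removed, all of grade II goes although only embolus and transfusion within it count as major, and deaths and unlisted serious events remain. The numerical examples also use rates chosen so that the totals cancel; they show that the effect is possible, not that it is likely.

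**Conclusion.** The point holds in a limited form. On the protocol's wording, the SAE outcome is a residual set that leaves out most serious surgical complications and admits milder, stay-prolonging forms of some of them: chiefly smaller bleeds without transfusion, observed pelvic haematomas and bedside-managed wound problems, where these are grade I. It should not be read alone as a comparison of serious harm, and its exemption from the no-significance rule invites that reading.

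The classification rests on the text alone. The size is unknown: it depends on how often grade I events prolong the stay in each arm, for which the protocol gives no figure. No sample size, error rate or primary conclusion changes. It merits correction because the tested count can mislead and the change is cheap.

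**What to change.** Reconcile the definitions table with sections 9.2, 9.3, 13.2 and 13.2.2, in one of two ways.

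(a) State that section 9.2 governs reporting only. For the between-arm comparison up to six weeks, count once per woman every event that meets the protocol's definition of serious, from SAE forms and the complication CRFs together. Cost: protocol wording, a derived variable and a new seriousness field on the complication CRFs. Those CRFs end at six weeks, so the combined count must end there too; extending it would mix full capture with residual capture. The reported rate will be higher.

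(b) Exclude surgical and anaesthetic complications other than death at every grade. Name the outcome SAEs other than surgical or anaesthetic complications, report it descriptively beside the primary and minor complication outcomes, and drop its exemption from the no-significance rule. Cost: wording only, with no new data.

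Under either option, say plainly that grade II-IV complications after six weeks enter neither the primary outcome nor the SAE comparison.

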9.3. Serious Adverse Adverts (SAE) non-CTIMPs

All events which meet the definition of serious, and that are not excluded above, will be collected and recorded as SAEs. These will be reported to the trials office immediately and within 24 hours of being made aware of the event.

9.4. Reporting period non-CTIMPs

Details of all AEs (except those listed above) will be documented and reported from the date of commencement of protocol defined treatment (entering the anaesthesia suite) until woman exits the study.

SAEs that are not excluded above but that are judged to be at least possibly related to the intervention must still be reported in an expedited manner irrespective of how long after intervention the event occurred.

9.5. Reporting period – At Site non-CTIMPs

9.5.1. Adverse Events

Depending on their nature, AEs should be recorded in the relevant place, i.e. on the relevant CRFs or on the SAE reporting form, with a record being kept on the site Adverse Event Log. Records of AEs should be returned to the BCTU trials team as soon as possible. The initial form should be returned to the BCTU by email. The data on the reporting form will be pseudo-anonymised by the person's trial number and their partial date of birth (month / year).

9.5.2. Serious Adverse Events

AEs defined as serious and which require reporting as an SAE should be reported on an SAE Form as soon as possible, but no later than 24 hours after the site has become aware of the adverse event. When completing the form, the PI will be asked to define the causality and the severity of the AE; according to the scale where a suspected causal relationship is definitely related; probably related; possibly related; unlikely to be related or unrelated.

Categorisation of causality (relatedness) for AEs and SAEs

Category	Definition	Causality
Definitely	There is clear evidence to suggest a causal relationship, and other possible contributing factors can be ruled out	Related
Probably	There is evidence to suggest a causal relationship, and the influence of other factors is unlikely	
Possibly	There is some evidence to suggest a causal relationship, however, the influence of other factors may have contributed to the event (e.g. the patient's clinical condition, other concomitant events or medication)	
Unlikely	There is little evidence to suggest there is a causal relationship; there is another reasonable explanation for the event (e.g. the patient's clinical condition, other concomitant events or medication)	Unrelated
Not related	There is no evidence of any causal relationship	

On becoming aware that a participant has experienced an SAE, the Investigator or their delegate should report the SAE to their own Trust in accordance with local practice and to the BCTU trials office.

To report an SAE to the BCTU trials office, the Investigator or their delegate must complete, date and sign the trial specific BCTU SAE form. The completed form should be scanned and emailed to the BCTU trials team using the trial mailbox address shown below as soon as possible and no later than 24 hours after first becoming aware of the event:

To report an SAE, email the SAE Form to:

[contact]

On receipt of an SAE form, the BCTU trials team will allocate each SAE a unique reference number and return this via email to the site as proof of receipt. If the site has not received confirmation of receipt of the SAE from BCTU or if the SAE has not been assigned a unique SAE identification number, the site should contact the BCTU trials team within one working day. The site and the BCTU trials team should ensure that the SAE reference number is quoted on all correspondence and follow-up reports regarding the SAE and filed with the SAE in the Site File.

Where an SAE Form has been completed by someone other than the Investigator, the original SAE form will be required to be countersigned by the Investigator to confirm agreement with the causality and severity assessments.

